4 = Completely disabled. Cannot carry on any self-care. Totally confined to bed or chair	xx (xx.xx)
5 = Dead	xx (xx.xx)
Patients performance grade changed, since last visit	
Yes	xx (xx.xx)
No	xx (xx.xx)

- The Capital "N" in the column header represents the total number of patients in Safety Analysis Set.
- The small "n" in summary statistic represents the total number of patients in the row category.
- Percentages are based on total number of patients in Safety Analysis Set.
- Programmer Note: Visit x- Visit 2 up to Visit 13.
- Source: Listing 16.1.10
- Table Name: xxxxx

Document Title:	Document ID:	BP04-01
Statistical Analysis Plan	Version Number:	
Statistical Analysis Plan	Effective Date:	

Table 14.2.1.1 Adverse Events (Safety Analysis Set)

	Durvalumab
	(N=xxx)
	n (%) E
Any Adverse Event	xx (xx.xx) xx
Any Serious Adverse Event	xx (xx.xx) xx
Any Treatment Emergent Adverse Event	xx (xx.xx) xx
Any Serious Treatment Emergent Adverse Event	xx (xx.xx) xx
Treatment Emergent Adverse Event related to IMP	xx (xx.xx) xx
Treatment Emergent Adverse Event leading to IMP discontinuation	xx (xx.xx) xx
Treatment Emergent Adverse Event leading to Death	xx (xx.xx) xx

- The capital "N" in the column header represents the total number of patients in Safety Analysis Set.
- The small "n' in summary represents the number of patients in row category.
- TEAE are those adverse events which occurred after first dose of study medication.
- Note: Adverse events were coded using MedDRA version xx.x
- If a Patient has multiple occurrences of an AE, the Patient is presented only once in the respective patient count column (n)
 for the corresponding AE. Events are counted each time in the event (E)
- Source: Listing 16.3.1.1 and Listing 16.3.1.2

Document Title:	Document ID:	BP04-01
Statistical Analysis Plan	Version Number:	3.1 25-Nov-2021
Statistical Analysis Plan	Effective Date:	

Table 14.2.1.2 Summary of Adverse Event (Safety Analysis Set)

	Durvalumab (N=xxx) n (%) E
Any Adverse Event reported	xx (xx.xx) xx
Severity as per CTCAE grade	
Mild	xx (xx.xx) xx
Moderate	xx (xx.xx) xx
Severe	xx (xx.xx) xx
Life Threatening	xx (xx.xx) xx
Death	xx (xx.xx) xx
Action Taken to Study Drug	
No Change in IP	xx (xx.xx) xx
IP Temporarily Interrupted	xx (xx.xx) xx
IP Permanently Discontinued	xx (xx.xx) xx
Other	xx (xx.xx) xx
Treatment Given	
Yes	xx (xx.xx) xx
No	xx (xx.xx) xx
Relationship with Study Drug	. ,
Related	xx (xx.xx) xx
Not Related	xx (xx.xx) xx
Outcome	
Resolved	xx (xx.xx) xx
Recovered/ Resolved with Sequelae	xx (xx.xx) xx
Recovering/ Resolving	xx (xx.xx) xx
Not Recovered/ Not Resolved	xx (xx.xx) xx
Fatal/ result in death	xx (xx.xx) xx
Unknown	xx (xx.xx) xx
Serious Adverse Event	
Yes	xx (xx.xx) xx
No	xx (xx.xx) xx
Seriousness Criteria	,
Death	xx (xx.xx) xx
Life-threatening	xx (xx.xx) xx
Inpatient hospitalization or prolongation of existing hospitalization	xx (xx.xx) xx
Proprietary and Confidential Document	Page 29 of 77

Document Title:	Document ID:	BP04-01
Sandindinal Amelusia Plan	Version Number:	3.1
Statistical Analysis Plan	Effective Date:	25-Nov-2021

Persistent or significant disability/ incapacity	xx (xx.xx) xx
Congenital anomaly/Birth Defect	xx (xx.xx) xx
Important medical events	xx (xx.xx) xx
Therapy Discontinued	
Yes	xx (xx.xx) xx
No	xx (xx.xx) xx

- The Capital "N" in the column header represents the total number Safety Analysis Set.
- The small "n" represents the total number of patients in the row category.
- All Percentages rows are based on number of Safety Analysis Set.
- TEAE = treatment-emergent adverse event; E = number of TEAE
- All Percentages are based on the total number of Safety Analysis Set.
- Source: Listing 16.3.1.1 and Listing 16.3.1.2

Table 14.2.1.3 Summary of Treatment Emergent Adverse Events by System Organ Class and Preferred Term (Safety Analysis Set)

	Durvalumab (N=xxx)
	n (%) E
Any TEAE	xx (xx.xx) xx
System Organ Class 1	xx (xx.xx) xx
Preferred Term 1	xx (xx.xx) xx
Preferred Term 2	xx (xx.xx) xx
System Organ Class 2	xx (xx.xx) xx
Preferred Term 1	xx (xx.xx) xx
Preferred Term 2	xx (xx.xx) xx

- TEAE = treatment-emergent adverse event; N = number of Patients in the Safety Analysis Set; n = number of Patients with TEAE; E = number of TEAE
- All Percentages are based on the number of patients in Safety Analysis Set.
- System Organ Class and Preferred term are coded using MedDRA version xx.x
- System Organ classes and preferred term are sorted by descending frequency. Preferred terms are sorted by descending frequency within system organ class.
- Source: Listing 16.3.1.1 and Listing 16.3.1.2

Document Title:	Document ID:	BP04-01
Statistical Applicate Plan	Version Number:	per: 3.1
Statistical Analysis Plan	Effective Date:	25-Nov-2021

Table 14.2.1.4 Summary of Serious Treatment Emergent Adverse Events by System Organ Class and Preferred Term (Safety Analysis Set)

	Durvalumab (N=xxx)
	n (%) E
Any Serious TEAE	xx (xx.xx) xx
System Organ Class 1	xx (xx.xx) xx
Preferred Term 1	xx (xx.xx) xx
Preferred Term 2	xx (xx.xx) xx
System Organ Class 2	xx (xx.xx) xx
Preferred Term 1	xx (xx.xx) xx
Preferred Term 2	xx (xx.xx) xx

TEAE = treatment-emergent adverse event; N = number of Patients in the Safety Analysis Set; n = number of Patients with TEAE; E = number of TEAE

Source: Listing 16.3.1.1 and Listing 16.3.1.2

⁻ All Percentages are based on the total number of patients in Safety Analysis Set.

⁻ System Organ Class and Preferred term are coded using MedDRA version xx.x

System Organ classes and preferred term are sorted by descending frequency. Preferred terms are sorted by descending frequency within system organ class.

Document Title:	Document ID:	BP04-01	
Statistical Analysis Plan	Version Number:	3.1	
	Effective Date:	25-Nov-2021	

Table 14.2.1.5 Summary of Treatment Emergent Adverse Events leading to permanent discontinuation by System Organ Class and Preferred Term (Safety Analysis Set)

	Durvalumab (N=xxx)	
	n (%) E	
Any TEAE leading to permanent discontinuation	xx (xx.xx) xx	
System Organ Class 1	xx (xx.xx) xx	
Preferred Term 1	xx (xx.xx) xx	
Preferred Term 2	xx (xx.xx) xx	
System Organ Class 2	xx (xx.xx) xx	
Preferred Term 1	xx (xx.xx) xx	
Preferred Term 2	xx (xx.xx) xx	

TEAE = treatment-emergent adverse event; N = number of Patients in the Safety Analysis Set; n = number of Patients with TEAE; E = number of TEAE

- All Percentages are based on the total number of patients in Safety Analysis Set.
- System Organ Class and Preferred term are coded using MedDRA version xx.x
- System Organ classes and preferred term are sorted by descending frequency. Preferred terms are sorted by descending frequency within system organ class.
- Source: Listing 16.3.1.1 and Listing 16.3.1.2

Document Title:	Document ID:	BP04-01	
Statistical Analysis Plan	Version Number:	3.1	
	Effective Date:	25-Nov-2021	

Table 14.2.1.6 Summary of Treatment Emergent Adverse Events leading to Death by System Organ Class and Preferred Term (Safety Analysis Set)

	Durvalumab (N=xxx)
	n (%) E
Any TEAE leading to death	xx (xx.xx) xx
System Organ Class 1	xx (xx.xx) xx
Preferred Term 1	xx (xx.xx) xx
Preferred Term 2	хх (хх.хх) хх
System Organ Class 2	xx (xx.xx) xx
Preferred Term 1	xx (xx.xx) xx
Preferred Term 2	xx (xx.xx) xx

TEAE = treatment-emergent adverse event; N = number of Patients in the Safety Analysis Set; n = number of Patients with TEAE; E = number of TEAE

- All Percentages are based on the total number of patients in Safety Analysis Set.
- System Organ Class and Preferred term are coded using MedDRA version xx.x
- System Organ classes and preferred term are sorted by descending frequency. Preferred terms are sorted by descending frequency within system organ class.
- Source: Listing 16.3.1.1 and Listing 16.3.1.2

Document Title:	Document ID:	BP04-01
Statistical Analysis Plan	Version Number:	3.1
	Effective Date:	25-Nov-2021

Table 14.2.1.7 Summary of Treatment Emergent Adverse Event by System Organ Class, Preferred Term and Severity (Safety Analysis Set)

	Durvalumab (N=xxx)					
	Mild	Mild Moderate Severe Life Threatening				
	n (%) E	n (%) E	n (%) E	n (%) E	n (%) E	
Any TEAE	xx (xx.xx) xx	xx (xx.xx) xx	xx (xx.xx) xx	xx (xx.xx) xx	xx (xx.xx) xx	
System Organ Class 1	xx (xx.xx) xx	xx (xx.xx) xx	xx (xx.xx) xx	xx (xx.xx) xx	xx (xx.xx) xx	
Preferred Term 1	xx (xx.xx) xx	xx (xx.xx) xx	xx (xx.xx) xx	xx (xx.xx) xx	xx (xx.xx) xx	
Preferred Term 2	xx (xx.xx) xx	xx (xx.xx) xx	xx (xx.xx) xx	xx (xx.xx) xx	xx (xx.xx) xx	
System Organ Class 2	xx (xx.xx) xx	xx (xx.xx) xx	xx (xx.xx) xx	xx (xx.xx) xx	xx (xx.xx) xx	
Preferred Term 1	xx (xx.xx) xx	xx (xx.xx) xx	xx (xx.xx) xx	xx (xx.xx) xx	xx (xx.xx) xx	
Preferred Term 2	xx (xx.xx) xx	xx (xx.xx) xx	xx (xx.xx) xx	xx (xx.xx) xx	xx (xx.xx) xx	

TEAE = treatment-emergent adverse event; N = number of Patients in the Safety Analysis Set; n = number of Patients with TEAE; E = number of TEAE

⁻ All Percentages are based on the total number of patients in Safety Analysis Set.

System Organ Class and Preferred term are coded using MedDRA version xx.x

System Organ classes and preferred term are sorted by descending frequency. Preferred terms are sorted by descending frequency within system organ class.

Source: Listing 16.3.1.1 and Listing 16.3.1.2

Document Title:	Document ID:	BP04-01
Statistical Analysis Plan	Version Number:	3.1
	Effective Date:	25-Nov-2021

Table 14.2.1.8 Summary of Treatment Emergent Adverse Event by System Organ Class and Preferred Term (Safety Analysis Set)

	Durvalumab	
	(N=xxx)	
	Related	
	n (%) E	
Any Related TEAE	xx (xx.xx) xx	
System Organ Class 1	xx (xx.xx) xx	
Preferred Term 1	xx (xx.xx) xx	
Preferred Term 2	xx (xx.xx) xx	
System Organ Class 2	xx (xx.xx) xx	
Preferred Term 1	xx (xx.xx) xx	
Preferred Term 2	xx (xx.xx) xx	

TEAE = treatment-emergent adverse event; N = number of Patients in the Safety Analysis Set; n = number of Patients with TEAE; E = number of TEAE

- All Percentages are based on the total number of patients in Safety Analysis Set.
- System Organ Class and Preferred term are coded using MedDRA version xx.x
- System Organ classes and preferred term are sorted by descending frequency. Preferred terms are sorted by descending frequency within system organ class.
- Source: Listing 16.3.1.1 and Listing 16.3.1.2

Table 14.2.1.9 Summary of Serious Treatment Emergent Adverse Event by System Organ Class and Preferred Term (Safety Analysis Set)

	Durvalumab
_	(N=xxx)
	Related
	n (%) E
Any Related Serious TEAE	xx (xx.xx) xx
System Organ Class 1	xx (xx.xx) xx
Preferred Term 1	xx (xx.xx) xx
Preferred Term 2	xx (xx.xx) xx
System Organ Class 2	xx (xx.xx) xx
Preferred Term 1	xx (xx.xx) xx
Preferred Term 2	xx (xx.xx) xx

TEAE = treatment-emergent adverse event; N = number of Patients in the Safety Analysis Set; n = number of Patients with TEAE; E = number of TEAE

System Organ classes and preferred term are sorted by descending frequency. Preferred terms are sorted by descending frequency within system organ class.

Proprietary and Confidential Document	Page 35 of 77
---------------------------------------	---------------

All Percentages are based on the total number of patients in Safety Analysis Set.

System Organ Class and Preferred term are coded using MedDRA version xx.x

Document Title:	Document ID:	BP04-01
Statistical Analysis Plan	Version Number:	3.1
	Effective Date:	25-Nov-2021

Source: Listing 16.3.1.1 and Listing 16.3.1.2

Table 14.2.1.10 Summary of Treatment Emergent Adverse Event by System Organ Class, Preferred Term and Relationship with Study Drug (Safety Analysis Set)

	Durvalumab							
	(N=xxx)							
		Resolve with Resolving Not Resolved Result in						
	Resolved	Sequelae			Death			
	n (%) E	n (%) E	n (%) E	n (%) E	n (%) E	n (%) E		
Any TEAE	xx (xx.xx) xx	xx (xx.xx) xx	xx (xx.xx) xx	xx (xx.xx) xx	xx (xx.xx) xx	xx (xx.xx) xx		
System Organ Class 1	xx (xx.xx) xx	xx (xx.xx) xx	xx (xx.xx) xx	xx (xx.xx) xx	xx (xx.xx) xx	xx (xx.xx) xx		
Preferred Term 1	xx (xx.xx) xx	xx (xx.xx) xx	xx (xx.xx) xx	xx (xx.xx) xx	xx (xx.xx) xx	xx (xx.xx) xx		
Preferred Term 2	xx (xx.xx) xx	xx (xx.xx) xx	xx (xx.xx) xx	xx (xx.xx) xx	xx (xx.xx) xx	xx (xx.xx) xx		
System Organ Class 2	xx (xx.xx) xx	xx (xx.xx) xx	xx (xx.xx) xx	xx (xx.xx) xx	xx (xx.xx) xx	xx (xx.xx) xx		
Preferred Term 1	xx (xx.xx) xx	xx (xx.xx) xx	xx (xx.xx) xx	xx (xx.xx) xx	xx (xx.xx) xx	xx (xx.xx) xx		
Preferred Term 2	xx (xx.xx) xx	xx (xx.xx) xx	xx (xx.xx) xx	xx (xx.xx) xx	xx (xx.xx) xx	xx (xx.xx) xx		

- TEAE = treatment-emergent adverse event; N = number of Patients in the Safety Analysis Set; n = number of Patients with TEAE; E = number of TEAE
- All Percentages are based on the total number of patients in Safety Analysis Set.
- System Organ Class and Preferred term are coded using MedDRA version xx.x
- System Organ classes and preferred term are sorted by descending frequency. Preferred terms are sorted by descending frequency within system organ class.
- Source: Listing 16.3.1.1 and Listing 16.3.1.2

Document Title:	Document ID:	BP04-01
Shakishing Angloria Plan	Version Number:	3.1
Statistical Analysis Plan	Effective Date:	25-Nov-2021

Table 14.3.1 Summary of Physical Examination (Safety Analysis Set)

	Durvalumab
	N = xx n (%)
Visit x	11 (70)
Patients Examination Done	
Yes	xx (xx.xx)
No	xx (xx.xx)
Missing	xx (xx.xx)
General Appearance	^^ (^^.^^)
Normal	xx (xx.xx)
Abnormal	xx (xx.xx)
If Abnormal	^^ (^^.^^)
NCS	xx (xx.xx)
CS	xx (xx.xx)
	** (**.**)
Respiratory Normal	w /w w/
Abnormal	xx (xx.xx)
If Abnormal	xx (xx.xx)
NCS	and the second
	xx (xx.xx)
CS Continuous I o	xx (xx.xx)
Cardiovascular	
Normal	xx (xx.xx)
Abnormal	xx (xx.xx)
If Abnormal	,
NCS	xx (xx.xx)
CS	xx (xx.xx)
Abdomen	
Normal	xx (xx.xx)
Abnormal	xx (xx.xx)
If Abnormal	
NCS	xx (xx.xx)
CS	xx (xx.xx)
Skin	
Normal	xx (xx.xx)
Abnormal	xx (xx.xx)
If Abnormal	
NCS	xx (xx.xx)
CS	xx (xx.xx)
HEENT	
Normal	xx (xx.xx)
Abnormal	xx (xx.xx)
If Abnormal	
NCS	xx (xx.xx)
CS	xx (xx.xx)
Neck	
Normal	xx (xx.xx)
Abnormal	xx (xx.xx)
Proprietary and Confidential Document	Page 37 of 77

Document Title:	Document ID:	BP04-01
Statistical Analysis Plan	Version Number:	3.1
	Effective Date:	25-Nov-2021

If Almontol	
If Abnormal	()
NCS	xx (xx.xx)
CS	xx (xx.xx)
Lymph Node	, ,
Normal	xx (xx.xx)
Abnormal	xx (xx.xx)
If Abnormal	
NCS	xx (xx.xx)
CS	xx (xx.xx)
Thyroid	
Normal	xx (xx.xx)
Abnormal	xx (xx.xx)
If Abnormal	
NCS	xx (xx.xx)
CS	xx (xx.xx)
Musculo-skeletal	
Normal	xx (xx.xx)
Abnormal	xx (xx.xx)
If Abnormal	
NCS	xx (xx.xx)
CS	xx (xx.xx)
Genital/Rectal	
Normal	xx (xx.xx)
Abnormal	xx (xx.xx)
If Abnormal	
NCS	xx (xx.xx)
CS	xx (xx.xx)
Neurological	
Normal	xx (xx.xx)
Abnormal	xx (xx.xx)
If Abnormal	
NCS	xx (xx.xx)
CS	xx (xx.xx)
Others	
Normal	xx (xx.xx)
Abnormal	xx (xx.xx)
If Abnormal	
NCS	xx (xx.xx)
CS	xx (xx.xx)
The Control WAII in the column hander common to the text of control of Coffee Analysis Coffee	

- The Capital "N" in the column header represents the total number Safety Analysis Set.
- The small "n" represents the total number of patients in the row category.
- All Percentages rows are based on number of Safety Analysis Set.
- Programmer Note: Visit x Visit 1 up to Visit 12.
- Source: Listing 16.3.2

Document Title:	Document ID:	BP04-01
Statistical Analysis Plan	Version Number:	3.1
	Effective Date:	25-Nov-2021

Table 14.3.2 Summary of Vital Sign (Safety Analysis Set)

	N = xx
Visit x	
Examination Done, n (%)	
Yes	xx (xx.xx)
No	xx (xx.xx)
Missing	xx (xx.xx)
Systolic Blood Pressure (mmHg)	
n	Xx
Missing	Xx
Mean (SD)	xx.x (xx.xx)
Median	xx.x
(min, max)	(xx.xx, xx.xx)
Diastolic Blood Pressure (mmHg)	
n	Xx
Missing	Xx
Mean (SD)	xx.x (xx.xx)
Median	xx.x
(min, max)	(xx.xx, xx.xx)
Pulse Rate (beats/min)	
n	Xx
Missing	Xx
Mean (SD)	xx.x (xx.xx)
Median	xx.x
(min, max)	(xx.xx, xx.xx)
Respiratory Rate (breaths/min)	
n	Xx
Missing	Xx
Mean (SD)	xx.x (xx.xx)
Median	xx.x
(min, max)	(xx.xx, xx.xx)
Temperature (°F)	
n	Xx
Missing	Xx
Mean (SD)	xx.x (xx.xx)
Median	xx.x
(min, max)	(xx.xx, xx.xx)
Oxygen Saturation (%)	
n	Xx
Missing	Xx
Mean (SD)	xx.x (xx.xx)
Median	xx.x
(min, max)	(xx.xx, xx.xx)
Weight (Kg)	
n	Xx
Missing	Xx

Page 39 of 77

Proprietary and Confidential Document

Document Title:	Document ID:	BP04-01
Statistical Applicate Plans	Version Number:	3.1
Statistical Analysis Plan	Effective Date:	25-Nov-2021

 Mean (SD)
 xx.x (xx.xx)

 Median
 xx.x

 (min, max)
 (xx.xx, xx.xx)

- The Capital "N" in the column header represents the total number Safety Analysis Set.
- The small "n" represents the total number of patients in the row category.
- Percentages in the "Examination Done" rows are based on number of Safety Analysis Set.
- SD = Standard Deviation, min=minimum, max=maximum
- Programmer Note: Visit x Visit 2 up to Visit 12.
- Source: Listing 16.3.3

Document Title:	Document ID:	BP04-01
Statistical Analysis Plan	Version Number:	3.1
	Effective Date:	25-Nov-2021

Table 14.3.3 Summary of 12-Lead Electrocardiogram (Safety Analysis Set)

	N = xx
Visit x	
Assessment Done, n (%)	
Yes	xx (xx.xx)
No	xx (xx.xx)
Missing	xx (xx.xx)
Heart rate (beats/min)	
n	Xx
Missing	Xx
Mean (SD)	xx.x (xx.xx)
Median	xx.x
(min, max)	(xx.xx, xx.xx)
QRS (ms)	
n	Xx
Missing	Xx
Mean (SD)	xx.x (xx.xx)
Median	XX.X
(min, max)	(xx.xx, xx.xx)
PR (ms)	
n	Xx
Missing	Xx
Mean (SD)	xx.x (xx.xx)
Median	xx.x
(min, max)	(xx.xx, xx.xx)
RR (ms)	
n	Xx
Missing	Xx
Mean (SD)	xx.x (xx.xx)
Median	xx.x
(min, max)	(xx.xx, xx.xx)
QT (ms)	
n	Xx
Missing	Xx
Mean (SD)	xx.x (xx.xx)
Median	xx.x
(min, max)	(xx.xx, xx.xx)
QTcF (ms)	
n	Xx
Missing	Xx
Mean (SD)	xx.x (xx.xx)
Median	xx.x
(min, max)	(xx.xx, xx.xx)

- The Capital "N" in the column header represents the total number Safety Analysis Set.
- The small "n" represents the total number of patients in the row category.
- Percentages in the "Assessment Done" rows are based on number of Safety Analysis Set.
- SD = Standard Deviation, min=minimum, max=maximum

	Document Title:	Document ID:	BP04-01
Chatletteel Academic Plans	Version Number:	3.1	
	Statistical Analysis Plan	Effective Date:	25-Nov-2021

Programmer Note: Visit x – Visit 2, Visit 6 and Visit 10.

Source: Listing 16.3.4

Document Title:	Document ID:	BP04-01
Shakishing Angloria Plan	Version Number:	3.1
Statistical Analysis Plan	Effective Date:	25-Nov-2021

Table 14.3.4.1 Summary of Haematology (Safety Analysis Set)

	N = xx
	n (%)
Visit x	
Sample Collected	
Yes	xx (xx.xx)
No	xx (xx.xx)
Missing	xx (xx.xx)
Haematocrit	
Normal	xx (xx.xx)
Abnormal	xx (xx.xx)
If Abnormal	
CS	xx (xx.xx)
NCS	xx (xx.xx)
Haemoglobin	
Normal	xx (xx.xx)
Abnormal	xx (xx.xx)
lf Abnormal	
CS	xx (xx.xx)
NCS	xx (xx.xx)
Basophils	•
Normal	xx (xx.xx)
Abnormal	xx (xx.xx)
f Abnormal	. ,
CS	xx (xx.xx)
NCS	xx (xx.xx)
Eosinophils	, ,
Normal	xx (xx.xx)
Abnormal	xx (xx.xx)
If Abnormal	,
CS	xx (xx.xx)
NCS	xx (xx.xx)
Monocytes	,
Normal	xx (xx.xx)
Abnormal	xx (xx.xx)
f Abnormal	
CS	xx (xx.xx)
NCS	xx (xx.xx)
Absolute Neutrophil Count	
Normal	xx (xx.xx)
Abnormal	xx (xx.xx)
If Abnormal	
CS	xx (xx.xx)
NCS	xx (xx.xx)
Platelet count	
Normal	xx (xx.xx)
Abnormal	xx (xx.xx)
f Abnormal	00 (00:00)
CS	xx (xx.xx)
NCS	xx (xx.xx)
Total Lymphocyte count	00 (00:00)
Proprietary and Confidential Document	Page 43 of 77

	Document Title:	Document ID:	BP04-01
Statistical Analysis Plan	Version Number:	3.1	
	Effective Date:	25-Nov-2021	

Normal	xx (xx.xx)
Abnormal	xx (xx.xx)
If Abnormal	
CS	xx (xx.xx)
NCS	xx (xx.xx)
Differential Lymphocyte count	
Normal	xx (xx.xx)
Abnormal	xx (xx.xx)
If Abnormal	
CS	xx (xx.xx)
NCS	xx (xx.xx)

- The Capital "N" in the column header represents the total number Safety Analysis Set.
- The small "n" represents the total number of patients in the row category.
- All Percentages rows are based on number of Safety Analysis Set.
- NCS=Abnormal Not Clinically Significant and CS= Abnormal Clinically Significant
- Programmer Note: Visit x Visit 2 up to Visit 12.
- Source: Listing 16.3.5

Document Title:	Document ID:	BP04-01
Statistical Analysis Plan	Version Number:	3.1
	Effective Date:	25-Nov-2021

Table 14.3.4.2 Summary of Serum Chemistry (Safety Analysis Set)

	N = xx
	n (%)
Visit x	
Sample Collected	
Yes	xx (xx.xx)
No	xx (xx.xx)
Missing	xx (xx.xx)
Albumin	
Normal	xx (xx.xx)
Abnormal	xx (xx.xx)
If Abnormal	
CS	xx (xx.xx)
NCS	xx (xx.xx)
Glucose	, ,
Normal	xx (xx.xx)
Abnormal	xx (xx.xx)
If Abnormal	
CS	xx (xx.xx)
NCS	xx (xx.xx)
Alkaline phosphatase	on funion)
Normal	xx (xx.xx)
Abnormal	xx (xx.xx)
If Abnormal	an (anian)
CS	xx (xx.xx)
NCS	xx (xx.xx)
Lactate dehydrogenase	^^ (^^.^^)
Normal	xx (xx.xx)
Abnormal	xx (xx.xx)
f Abnormal	** (**.**)
CS	yy /yy yyl
NCS	xx (xx.xx)
Alanine aminotransferase	xx (xx.xx)
Normal	
Abnormal	xx (xx.xx)
	xx (xx.xx)
f Abnormal	
CS	xx (xx.xx)
NCS	xx (xx.xx)
Lipase	
Normal	xx (xx.xx)
Abnormal	xx (xx.xx)
lf Abnormal	
CS	xx (xx.xx)
NCS	xx (xx.xx)
Aspartate amin-otransferase	
Normal	xx (xx.xx)
Abnormal	xx (xx.xx)
f Abnormal	
CS	xx (xx.xx)
NCS	xx (xx.xx)
Magnesium	
Proprietary and Confidential Document	Dogo 45 of 77
Proprietary and Confidential Document	Page 45 of 77

Document Title:	Document ID:	BP04-01
Statistical Analysis Plan	Version Number:	3.1
	Effective Date:	25-Nov-2021

Proprietary and Confidential Document	Page 46 of 77
Proprietary and Confidential Desument	Dago 46 -677
CS	xx (xx.xx)
If Abnormal	
Abnormal	xx (xx.xx)
Normal	xx (xx.xx)
Total protein	
NCS	xx (xx.xx)
CS	xx (xx.xx)
If Abnormal	
Abnormal	xx (xx.xx)
Normal	xx (xx.xx)
Chloride	
NCS	xx (xx.xx)
CS	xx (xx.xx)
If Abnormal	, ,
Abnormal	xx (xx.xx)
Normal	xx (xx.xx)
Total bilirubin	,
NCS	xx (xx.xx)
CS	xx (xx.xx)
If Abnormal	an (anian)
Abnormal	xx (xx.xx)
Normal	xx (xx.xx)
NCS Calcium	xx (xx.xx)
CS NCS	xx (xx.xx)
If Abnormal	
Abnormal	xx (xx.xx)
Normal	xx (xx.xx)
Sodium	
NCS	xx (xx.xx)
CS	xx (xx.xx)
If Abnormal	
Abnormal	xx (xx.xx)
Normal	xx (xx.xx)
Bicarbonate	
NCS	xx (xx.xx)
CS	xx (xx.xx)
If Abnormal	
Abnormal	xx (xx.xx)
Normal	xx (xx.xx)
Potassium	
NCS	xx (xx.xx)
CS	xx (xx.xx)
If Abnormal	
Abnormal	xx (xx.xx)
Normal	xx (xx.xx)
Amylase	· · · · · · · · · · · · · · · · · · ·
NCS	xx (xx.xx)
CS	xx (xx.xx)
If Abnormal	(
Abnormal	xx (xx.xx)
Normal	xx (xx.xx)

Document Title:	Document ID:	BP04-01
Statistical Analysis Plan	Version Number:	3.1
	Effective Date:	25-Nov-2021

NCS	xx (xx.xx)
Creatinine Clearance	na (man)
Normal	xx (xx.xx)
Abnormal	xx (xx.xx)
If Abnormal	in (initial)
CS	xx (xx.xx)
NCS	xx (xx.xx)
Urea / Blood Urea/ Nitrogen	,
Normal	xx (xx.xx)
Abnormal	xx (xx.xx)
If Abnormal	, , , , , , , , , , , , , , , , , , , ,
CS	xx (xx.xx)
NCS	xx (xx.xx)
Gamma glutamyl transferase	
Normal	xx (xx.xx)
Abnormal	xx (xx.xx)
If Abnormal	
CS	xx (xx.xx)
NCS	xx (xx.xx)
Uric acid	
Normal	xx (xx.xx)
Abnormal	xx (xx.xx)
If Abnormal	
CS	xx (xx.xx)
NCS	xx (xx.xx)

- The Capital "N" in the column header represents the total number Safety Analysis Set.
- The small "n" represents the total number of patients in the row category.
- All Percentages rows are based on number of Safety Analysis Set.
- NCS=Abnormal Not Clinically Significant and CS= Abnormal Clinically Significant
- Programmer Note: Visit x Visit 2 up to Visit 12.
- Source: Listing 16.3.6

Document Title:	Document ID:	BP04-01
Statistical Analysis Plan	Version Number:	3.1
	Effective Date:	25-Nov-2021

Table 14.3.4.3 Summary of Urine Routine and Microscopy (Safety Analysis Set)

	N = xx
	n (%)
Visit x	
Sample Collected	
Yes	xx (xx.xx)
No	xx (xx.xx)
Missing	xx (xx.xx)
Specific gravity	
Normal	xx (xx.xx)
Abnormal	xx (xx.xx)
If Abnormal	
CS	xx (xx.xx)
NCS	xx (xx.xx)
pH	
Normal	xx (xx.xx)
Abnormal	xx (xx.xx)
lf Abnormal	
CS	xx (xx.xx)
NCS	xx (xx.xx)
Glucose	,
Normal	xx (xx.xx)
Abnormal	xx (xx.xx)
lf Abnormal	,
CS	xx (xx.xx)
NCS	xx (xx.xx)
Ketones	
Normal	xx (xx.xx)
Abnormal	xx (xx.xx)
f Abnormal	an (aman)
CS	xx (xx.xx)
NCS	xx (xx.xx)
Bilirubin	an (anian)
Normal	xx (xx.xx)
Abnormal	xx (xx.xx)
f Abnormal	~~ (~~~~)
CS	xx (xx.xx)
NCS	xx (xx.xx)
Urobilinogen	** (**.**)
Normal	xx (xx.xx)
Abnormal	xx (xx.xx) xx (xx.xx)
If Abnormal	** (**.**)
CS CS	vu lvu vul
NCS	xx (xx.xx)
RBC	xx (xx.xx)
Normal	www.free.com
Abnormal	xx (xx.xx)
	xx (xx.xx)
If Abnormal	t
CS NCS	xx (xx.xx)
NCS	xx (xx.xx)
Dysmorphic Red Blood Cells	
Proprietary and Confidential Document	Page 48 of 77

Document Title:	Document ID:	BP04-01
Statistical Analysis Plan	Version Number:	3.1
	Effective Date:	25-Nov-2021

Normal	xx (xx.xx)
Abnormal	xx (xx.xx)
If Abnormal	
CS	xx (xx.xx)
NCS	xx (xx.xx)
Pus Cells	
Normal	xx (xx.xx)
Abnormal	xx (xx.xx)
If Abnormal	
CS	xx (xx.xx)
NCS	xx (xx.xx)
Crystals	
Normal	xx (xx.xx)
Abnormal	xx (xx.xx)
If Abnormal	. ,
CS	xx (xx.xx)
NCS	xx (xx.xx)
Casts	,
Normal	xx (xx.xx)
Abnormal	xx (xx.xx)
If Abnormal	, ,
CS	xx (xx.xx)
NCS	xx (xx.xx)
Epithelial Cells	,
Normal	xx (xx.xx)
Abnormal	xx (xx.xx)
If Abnormal	
CS	xx (xx.xx)
NCS	xx (xx.xx)
Protein	,
Normal	xx (xx.xx)
Abnormal	xx (xx.xx)
If Abnormal	
CS	xx (xx.xx)
NCS	xx (xx.xx)

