The Treatment Phase will extend from start of Week 0 to end of week 20, Day 141; or until study drug discontinuation due to either disease progression or unacceptable toxicity; or other reasons whichever occurs earlier, as listed in Section 7.1. Patients may continue to receive durvalumab as long they are continuing to show clinical benefit, as judged by the investigator, and in the absence of discontinuation criteria.

Post-trial access

Patients who are observed to receive clinical benefit from durvalumab at the end of week 20 may continue get the drug free of cost (provided by AstraZeneca) to all the responding patients until unacceptable toxicity/disease progression or as per the decision of the treating physician

Safety Evaluations

Safety evaluations will include adverse event monitoring, physical examinations, ECG monitoring, clinical laboratory parameters (hematology and biochemistry), vital sign measurements, and WHO performance status and death as observed by the investigator. Based on the previous human experience with durvalumab, in vitro studies, and animal toxicological

Study Code - D133HC00003 Version 4.1, Date: 12 October 2022 findings immune mediated pneumonitis hepatitis colitis a

findings, immune mediated pneumonitis, hepatitis, colitis and endocrinopathies will be closely monitored. Any of the safety monitoring assessments may be performed more frequently, and adverse events should be evaluated by the investigator according to the standard practice if clinically indicated.

Statistical methods

Sample Size Justification

The primary endpoint of the trial is to demonstrate the safety profile of durvalumab in routine clinical practice as assessed by the incidence of adverse events (AEs) (Serious and Non-serious AEs) observed during trial. Based on the Durvalumab historic data, estimated proportion of 31% for adverse events prevalence rate. With a sample size of 83, would be able to achieve the 10% precision of the estimates with the 95% level of confidence. Approximately 120 participants will be screened to achieve around 100 participants enrolled in the study.

Scenario#	estimated proportion	Precision	Confidence level	Required sample size
1	31%	.15	95%	37
2	31%	.14	95%	42
3	31%	.13	95%	49
4	31%	.12	95%	58
5	31%	.11	95%	68
6	31%	.10	95%	83

Hypothesis

No formal hypothesis testing will be conducted.

Statistical Analysis

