8.1.2 Physical examinations

For timing of individual measurements refer to the study schedules (Table 1 [Screening and the Treatment Period]

A complete physical examination will be performed and will include an assessment of the following (as clinically indicated): general appearance, respiratory, cardiovascular, abdomen, skin, head and neck (including ears, eyes, nose and throat), lymph nodes, thyroid, musculo-skeletal (including spine and extremities), genital/rectal and neurological systems.

Performance status will be assessed using WHO performance status.

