(min, max) (xx.xx, xx.xx) Performance status at time of initiation of CRT Xx n Xx Missing Xx Mean (SD) xx.x (xx.xx) Median xx.x (min, max) (xx.xx, xx.xx)	• •	xx.x (xx.xx)
Performance status at time of initiation of CRT Xx n Xx Missing Xx Mean (SD) xx.x (xx.xx) Median xx.x (min, max) (xx.xx, xx.xx)	Median	xx.x
n Xx Missing Xx Mean (SD) xx.x (xx.xx) Median xx.x (min, max) (xx.xx, xx.xx)	(min, max)	(xx.xx, xx.xx)
Missing Xx Mean (SD) xx.x (xx.xx) Median xx.x (min, max) (xx.xx, xx.xx)	Performance status at time of initiation of CRT	
Mean (SD) xx.x (xx.xx) Median xx.x (min, max) (xx.xx, xx.xx)	n	Xx
Median xx.x (min, max) (xx.xx, xx.xx)	Missing	Xx
(min, max) (xx.xx, xx.xx)	, ,	xx.x (xx.xx)
	Median	xx.x
		(xx.xx, xx.xx)

- The Capital "N" in the column header represents the total number Enrolled Analysis Set.
- The small "n" represents the total number of patients in the row category.
- Percentages are based on total number of Enrolled Analysis Set.
- SD = Standard Deviation, min=minimum, max=maximum
- Source: Listing 16.1.9.1 and Listing 16.1.9.2

Document Title:	Document ID:	BP04-01
Statistical Analysis Dlan	Version Number:	3.1 25-Nov-2021
Statistical Analysis Plan	Effective Date:	

Table 14.1.8 Summary of WHO Performance Status (Safety Analysis Set)

	N = xx
Visit 1	
WHO Performance Grade	
0 = Fully active, able to carry on all pre-disease performance without restriction	xx (xx.xx)
1 = Restricted in physically strenuous activity but ambulatory and able to carry out work of a light or sedentary nature	xx (xx.xx)
2 = Restricted in physically strenuous activity but ambulatory and able to carry out work of a light or sedentary nature, e.g., light housework, office work	xx (xx.xx)
3 = Capable of only limited self-care, confined to bed or chair more than 50% of waking hours	xx (xx.xx)
4 = Completely disabled. Cannot carry on any self-care. Totally confined to bed or chair	xx (xx.xx)
5 = Dead	xx (xx.xx)
Visit x	
WHO Performance Grade	
0 = Fully active, able to carry on all pre-disease performance without restriction	xx (xx.xx)
1 = Restricted in physically strenuous activity but ambulatory and able to carry out work of a light or sedentary nature	xx (xx.xx)
2 = Restricted in physically strenuous activity but ambulatory and able to carry out work of a light or sedentary nature, e.g., light housework, office work	xx (xx.xx)
3 = Capable of only limited self-care, confined to bed or chair more than 50% of waking hours	xx (xx.xx)

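### SAP Table 14.1.8 gives WHO grade 2 the grade 1 definition and leaves a level before grade 3 undefined, so its separate grade 1 and grade 2 counts cannot be interpreted as labelled

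*SAP*

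**What the plan says.** The protocol synopsis (Section 1.2, Safety Evaluations) names performance status among the safety evaluations: "vital sign measurements, and WHO performance status and death as observed by the investigator". The Schedule of Activities (Table 1) has it at Visits 1 to 12. Protocol Section 8.1.2 names the instrument and nothing more: "Performance status will be assessed using WHO performance status". The protocol does not define the grades.

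The only grade definitions are the row labels of the mock shell SAP Table 14.1.8, given once for Visit 1 and again for the later visits:

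- Grade 1: "1 = Restricted in physically strenuous activity but ambulatory and able to carry out work of a light or sedentary nature".
- Grade 2 opens with "2 = Restricted in physically strenuous activity but ambulatory and able to carry out work of a light or sedentary nature" and its full ending is "able to carry out work of a light or sedentary nature, e.g., light housework, office work".
- Grade 3: "3 = Capable of only limited self-care, confined to bed or chair more than 50% of waking hours".

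The shell closes with a Yes/No item, "Patients performance grade changed, since last visit". Listing 16.1.10 gives the numeric grade and a change flag by patient and visit. SAP Table 14.1.7 summarises "Performance status at time of initiation of CRT" as a continuous variable: n, missing, mean (SD), median and range.

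**The concern.** Categories in a frequency table should be mutually exclusive and should cover every patient. Here two adjacent rows share one definition, and the next row starts well below them. A reader of the study report who sees counts move from row 1 to row 2 could not tell from the table what loss of function that represents.

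The trial's only objective is safety, and performance status is a named safety evaluation with twelve scheduled assessments. The change item does not help. It pools improvement with worsening and, because the shell counts death as grade 5, it can pool death with both.

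**Working it through.** No planned figure depends on performance status, so the check is a comparison of wording.

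**1. Grade 1 against grade 2.** The grade 1 definition has 19 words. All 19 open the grade 2 definition in the same order. What remains is a short phrase giving housework and office work as examples. Those examples illustrate light or sedentary work, which grade 1 already allows, and set no lower level of function. Every patient who fits grade 2 therefore also fits grade 1.

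**2. Grade 2 against grade 3.** Grade 2 as labelled requires the ability to do light work. Grade 3 requires both limited self-care and more than half of waking hours in bed or chair. A patient who cannot do light work, but who has full self-care or spends half the waking day or less in bed or chair, fits neither label.

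**3. Extraction error.** The same wording stands in both blocks of the table, and the added phrase reads coherently. A fault in reading the PDF is unlikely.

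**4. Other definitions.** Protocol Sections 1.2 and 8.1.2, Table 1 and SAP Listing 16.1.10 name, schedule or list the grade. None defines it.

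**5. Effect on the recorded data.** There are two cases, and the documents do not say which applies.

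| How sites grade | Recorded grades | Table 14.1.8 |
|---|---|---|
| On the named WHO scale, correctly worded | Not affected; 0 patients misgraded | Counts valid, grade 2 label wrong |
| On eCRF text that repeats the table's wording | Grades 1 and 2 not separable at entry; at most all patients in those grades misgraded | Counts and label both unreliable |

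The documents give no distribution of grades. If 40% to 70% of about 100 patients were in grades 1 or 2 (an assumption), the second case would put 0.40 × 100 = 40 to 0.70 × 100 = 70 patients per visit in two rows that the text cannot separate. In the first case the number is 0.

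**6. Change row.** The item records only whether the grade changed since the last visit, and the shells include no shift table. Even with correct labels, Table 14.1.8 would not show how many patients worsened. The visit-level grades needed for that are already collected.

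**7. Sample size.** The planned 83 comes from the adverse event proportion alone: 1.96² × 0.31 × 0.69 / 0.10² = 82.17, rounded up to 83. Performance status does not enter.

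**The case against.** The strongest reply is that Table 14.1.8 is an output shell and not the grading instrument. The protocol sends investigators to a named scale. Grades 1 and 2 keep separate numbers in the table, and Listing 16.1.10 shows the grade for each patient at each visit. If sites graded on the named scale, a move from 1 to 2 is recorded and traceable, and only a row label is wrong. This stands. A reader might infer from the duplicated label that such moves cannot be identified, or that 40 to 70 patients are misgraded. The documents support neither inference, because both need the eCRF to carry the same text and the eCRF is not among them. The change row is likewise wrong in content only in that case.

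It can also be said that performance status has little weight here. It is not in the primary endpoint (Protocol Section 3, SAP 6.1.1) and is not among the evaluations in SAP 6.3.1. No eligibility criterion, discontinuation criterion or Appendix D entry uses it, and nothing is tested. This is correct and limits the consequence. It does not excuse a wrong definition in a results table for a named safety evaluation.

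Finally, a worsened / unchanged / improved row is an addition to the plan, and the mean (SD) in Table 14.1.7 comes with median and range for a characteristic that predates study treatment. The first is an addition, but it uses data in hand and gives the table the direction of change that it lacks. The second is fair, so that item is optional.

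**Conclusion.** The labelling error is certain on the face of the SAP: grades 1 and 2 share a definition, and a level of function before grade 3 has none. As labelled, the separate grade 1 and grade 2 counts in Table 14.1.8 cannot be interpreted.

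The effect on the data is open. The number of patients misgraded through the overlap lies between 0, if sites used the correctly worded scale, and all those in grades 1 or 2, if the eCRF repeats the SAP text. The upper end is a ceiling and not an estimate. The primary endpoint and the sample size do not change in either case.

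Separately, and whatever the labels say, the planned change row gives no direction, so the table cannot show deterioration. Both points should be corrected before the tables are produced.

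**What to change.** 1. In both blocks of SAP Table 14.1.8, replace the grade 2 label with the grade 2 wording of the WHO scale named in Protocol Section 8.1.2, copied from that scale. Confirm that grades 1, 2 and 3 then neither overlap nor leave a gap.
2. Check the performance status text on the eCRF. If it is correct, nothing more is needed. If it repeats the SAP wording, correct it and have sites re-confirm grades 1 and 2 from source.
3. Replace or supplement the Yes/No change row with worsened / unchanged / improved from a stated pre-dose baseline: Visit 2, or Visit 1 if Visit 2 is missing. The schedule does not say that the Visit 2 grade is taken before the infusion, so the SAP should define this. Show death on its own line.
4. Optional and minor: in Table 14.1.7, present performance status at the start of chemoradiation as n (%) per grade, to match Table 14.1.8.

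Items 1, 3 and 4 are shell edits and light programming on data already collected. Item 2 is a single document check. It becomes costly only if the eCRF text is wrong, because sites would then have to go back to source for past visits.
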